WHO	World Health Organization
ZBPI	Zoster Brief Pain Inventory

CONFIDENTIAL

1. Source Documents

The Statistical Analysis Plan (SAP) was written based on the following documentation:

Document	Date	Version
Protocol	14 September 2020	Final
Protocol Amendment	23 October 2020	1
Protocol Amendment	03 March 2021	2
Protocol Amendment	15 April 2021	2.1
Protocol Amendment	15 October 2021	3
Electronic case report form (eCRF)	02 December 2020	Final

2. Protocol Details

2.1 Study Objectives

2.1.1 Primary Objective

The primary objective of this study is to evaluate the efficacy of LX9211 in reducing pain related to postherpetic neuralgia (PHN).

2.1.2 Secondary Objective(s)

The secondary objective of this study is to assess other effects and patient-reported outcomes of LX9211 versus placebo during, and following, the Week 6 double-blind Treatment Period.

2.1.3 Other Objective(s)

Other objectives (endpoints) of this study are:

- Change from Baseline to Week 6 in the Neuropathic Pain Symptom Inventory (NPSI)
- Change from Baseline to each week in the average daily pain score (ADPS), based on Question 5 of the Zoster Brief Pain Inventory (ZBPI)
- Proportion of patients with $\geq 30\%$ reduction from Baseline in ADPS, based on Question 5 of the ZBPI by week
- Proportion of patients with $\geq 50\%$ reduction from Baseline in ADPS, based on Question 5 of the ZBPI by week
- Cumulative distribution function of percent change in ADPS based on Question 5 of the ZBPI from Baseline to Week 6 comparing the LX9211 treatment group to placebo

- Cumulative distribution function of percent change in ADPS based on Question 5 of the ZBPI from Week 6 to Week 11 comparing the LX9211 treatment group to placebo
- To evaluate plasma levels of LX9211 in patients with PHN.
- Safety will be assessed by adverse events (AEs), vital signs, electrocardiogram (ECG) findings, and laboratory parameters.

2.2 Overall Study Design

This is a Phase 2, multicenter, randomized, double-blind, placebo-controlled, parallel-group study in patients with PHN.

Scheduled study visits in the clinic will occur during Screening; at the initiation of the 2-week single-blind placebo Run-in Period; on Day 1 (Baseline), and during Weeks 2, 4, and 6 of the double-blind Treatment Period, and Week 11 of the single-blind Safety Follow-up Period.

Male or female patients ≥ 18 years of age, with prior herpes zoster skin rash and PHN pain persisting for ≥ 3 months after healing of the herpes zoster skin rash who meet all inclusion and no exclusion criteria are eligible for enrollment.

Eligible patients may continue use of 1 medication prescribed for PHN including pregabalin, gabapentin, and tricyclic antidepressant medications, as long as they have been at stable doses for ≥ 1 month prior to Screening and are willing to maintain their doses for the duration of the study. Patients taking more than 1 permitted concomitant medication for the treatment of PHN and unable to washout of all but 1 of these treatments for the duration of the study are not eligible. Use of any new medications, prescribed or over-the-counter for treatment of PHN pain, is not permitted during the course of the study. Use of any opioid medications for the management of PHN within the 2 months prior to Screening is not permitted. Brief use (< 1 week) of opioid medication for management of non-PHN acute pain ≥ 2 months prior to the Screening Visit is permitted.

Screening Period: After signing the Informed Consent Form (ICF), all patients will enter a Screening Period of up to 2 weeks. Patients using non-opioid medications that are prohibited by the protocol must discontinue or washout these medications as directed by the protocol prior to entering the Screening period. Following confirmation of eligibility criteria, patients will enter the following study periods:

Run-in Period: After meeting Screening eligibility criteria, patients will enter a 2-week single-blind Run-in Period. On Day 1 of the Run-in period, patients will be administered 4 tablets of single-blind study drug at the site. For the remaining duration of the Run-in Period, patients will take a single tablet of study drug every morning. Each evening patients will rate and record the intensity of their PHN pain based on Question 5 of the ZBPI by answering the question "Please rate your pain by indicating the one number that best describes your pain on the average in the

last 24 hours”, on the 11-point numerical rating scale (0 [No Pain] to 10 [Pain as bad as you can imagine]). The ADPS will be calculated using all available daily pain diary data. The mean value of the ADPS derived over Week 2 will serve as the Baseline measure used for analyses. In order to qualify for randomization, patients must complete $\geq 70\%$ of the daily pain diary entries during the second week of the Run-in Phase, meet criteria for moderate to severe pain, and demonstrate $\geq 80\%$ compliance with taking the expected amount of placebo tablets during the Run-in Period. During the Run-in Period patients will not be allowed to use any rescue medication. On the morning of the Run-in Visit, patients may consume a light meal prior to the visit. **Note:** Patients who fail Screening due to laboratory values may have those assessments repeated and be rescreened once after discussion with the Sponsor’s Medical Monitor.

Randomization/Double-blind Treatment Period: Patients who successfully complete the 2-week single-blind placebo Run-in Period and meet all other eligibility criteria will enter the 6-week double-blind Treatment Period. Patients will be randomly assigned in a 1:1 ratio between the following 2 treatment groups:

- **Group 1:** LX9211 200 mg* / 20 mg**, once daily (qd)
- **Group 2:** Placebo, qd matching loading and maintenance doses

* Loading dose (Day 1)

** Maintenance dose (Day 2 – Week 6 Visit)

Implementation of the treatment randomization schedule will be centralized. A 1:1 ratio for assigning patients between the treatment groups will be accomplished by use of randomly permuted blocks of fixed size.

On Day 1, patients will be assigned to LX9211 or placebo, to be given as a loading dose at the clinic. Patients will remain at the clinic for observation for 2 hours following dosing. At 2 hours, orthostatic vital signs will be obtained (heart rate and blood pressure) after which time patients may be released and a 2-hour postdose blood draw will occur.

The loading dose will be followed by a daily maintenance dose taken at home in the morning on Day 2 through the Week 6 Visit. **Note:** On days of the clinic visits, patients will refrain from taking their daily dose until after the visit.

Each evening during the double-blind Treatment Period, patients will be required to rate and record their average daily severity of their PHN over the previous 24 hours using Question 5 of ZBPI, record the use of rescue medication (acetaminophen), and rate the interference with sleep using Question 9F of the ZBPI. The ADPS will be calculated using all available data, however, a minimum of 4 days (consecutive or nonconsecutive) from the last week prior to each clinic visit is required for the calculation.

On the day of randomization, patients will also receive a bottle of acetaminophen. If a patient is unable to tolerate their PHN, they are encouraged to discuss treatment options with the Investigator. At the Investigator's direction, the patient may be permitted to take acetaminophen (up to a maximum of 3 grams per day) as a rescue medication. If rescue medication does not provide adequate pain relief, the patient may discontinue from further participation in the study after consultation with the Investigator. Patients who discontinue prior to completion of the Week 6 Visit will not be replaced.

Patients discontinuing the study prior to completion of the Week 6 Visit should be encouraged to return for the Week 6 Visit assessments and complete the Safety Follow-up Visit 5 weeks later.

[figure not shown]
Safety Follow-up Period: Following completion of the 6-week double-blind Treatment Period, all patients will enter the 5-week single-blind Safety Follow-up Period. During this period, patients will dose with 1 tablet of single-blind study drug every morning taken at home. Each evening patients will continue to rate and record the average severity of their PHN over the previous 24 hours using Question 5 of the ZBPI, record the use of rescue medication (acetaminophen), and rate the interference with sleep using the ZBPI.

Blood samples for the determination of plasma LX9211 trough levels (C_{trough}) will be drawn predose on Day 1 and at Weeks 2, 4, 6, and 11. Blood samples will be drawn 2 hours after dosing on Day 1 for the determination of plasma 2-hour levels (C_{p2hr}).

[REDACTED]

Optional Substudy: During the Screening Visit, patients may choose to participate in an optional substudy. The optional substudy is a qualitative patient interview, which will include approximately 30 patients. The interview will be conducted over the telephone and is designed to gain insight and understanding of patients' experiences with symptoms of PHN and to assess the relevance and clinical meaningfulness of symptom improvements (eg, reduction in pain) with LX9211 treatment.

The study design is presented in the diagram below:

2.3 Sample Size and Power

The proposed sample size is derived by satisfying the original design assumptions made for the primary efficacy endpoint. It is assumed that the difference in treatment group means is 0 under the null hypothesis (H_0) and is unequal to 0 under the alternative hypothesis (H_1); a 2-sided hypothesis under test. Under the H_1 , the difference in group means of LX9211 minus placebo is expected to be -0.8 units with a common standard deviation (SD) of 1.0 units. These assumptions yield an effect size of 0.8. The effect size is the absolute value of the difference in treatment group means divided by the common SD of that difference. A uniform dropout rate of 0.15 is anticipated, and adjustment of the effect size for this rate results in an estimate 0.68; the adjusted difference in group means is equal to -0.8 units x 0.85 = -0.68. For a 2-sided test sized at $\alpha = 0.05$, 37 patients per treatment group are required under a 1:1 randomization ratio to detect the stated treatment difference under H_1 with statistical power equal to 82.27% under a single stage design. The total planned N = 74 patients.

This study is designed as a group sequential trial with 1 interim look at the 50% information time point and a final analysis at 100%. A non-binding futility boundary will be used to test for futility of the primary endpoint. The futility boundary is 1-

sided with $\alpha = 0.025$ and for the parameters specified, a power estimate of 82.53% is derived.

Sample Size Reestimation

Due to the uncertainty in the outcome for the primary endpoint analysis in this population, an unblinded SSR adaptation will be implemented at the time of the futility interim analysis. This will occur when the first 38 patients (rounded up from 37) have been accrued and followed thru Week 6 or dropped out early from the trial (whichever event happens first). Should a patient drop out early in the study, but return for the Week 6 visit, the Week 6 data will be used in the analysis. The Chen-DeMets-Lan method will be used for the unblinded SSR since it requires minimal change from a group sequential test. This method requires specification for a number of criteria related to the allowable conditions for increasing the sample size that ensures that ordinary group sequential methods can be applied while seeing that the overall error is not inflated compared to the original group sequential design. The 2 primary conditions which are required and satisfied in the SSR for this study are that (a) the SSR is made at the penultimate look, and (b) the conditional power at the penultimate look occurs between 50% and 82.53% (the original specified power). The SSR is linked to the projected effect size falling within this "promising" or "favorable" range of conditional power. Having satisfied these 2 main conditions, the Type I error rate after increasing the sample size until the conditional power equals the original target power will not be greater than the Type I error from the originally proposed design.

To derive the reestimated number of patients at the interim analysis, a simulation will be made that: inputs the observed group mean difference and its common standard deviation, input a value for the maximum total number of patients ($E[\text{Max}]$) equal to 148 patients and, specify a reestimation rule as the Exact E method. The Exact E method increases the patient number total until the desired conditional power is achieved.

3. Efficacy and Safety Variables

3.1 Primary Efficacy Endpoint

The primary efficacy endpoint is the change from Baseline (Week 2 of the Run-in Period) to Week 6 in ADPS, based on Question 5 of the ZBPI, the 11-point numerical rating scale (0 [No Pain] to 10 [Pain as bad as you can imagine]) of LX9211 compared to placebo.

3.2 Secondary Efficacy Endpoints

The secondary efficacy endpoints are to be assessed in LX9211 compared to placebo for each of the following listed below:

- Change from Baseline to Week 6 in pain interfering with sleep based on Question 9F of the ZBPI "Indicate the one number that describes how, in the past 24-hours shingles pain has interfered with your: Sleep (0 [Does not interfere] to 10 [Completely interferes])."
- Proportion of patients with $\geq 30\%$ reduction in pain intensity in ADPS based on Question 5 of the ZBPI from Baseline to Week 6
- Proportion of patients with $\geq 50\%$ reduction in pain intensity in ADPS based on Question 5 of the ZBPI from Baseline to Week 6
- Change from Baseline to Week 6 in interference in General Activity, Mood, Walking Ability, Normal Work (includes both outside the home and housework), Relations with other people, Sleep, and Enjoyment of Life interference based on the Questions 9A-G of the ZBPI
- Proportion of patients discontinuing treatment due to lack of efficacy defined as increase in ADPS from Baseline of $\geq 30\%$ based on Question 5 of the ZBPI
- Patient Global Impression of Change (PGIC) at Week 6
- Time to loss of efficacy from Week 6 to Week 11 among patients achieving $\geq 30\%$ reduction in pain intensity in ADPS based on Question 5 of the ZBPI at Week 6

3.3 Other Efficacy Endpoints

The other efficacy endpoints are to be assessed in LX9211 compared to placebo for each of the following listed below:

- Change from Baseline to Week 6 in the NPSI
- Change from Baseline to each week in ADPS, based on Question 5 of the ZBPI
- Proportion of patients with $\geq 30\%$ reduction from Baseline in ADPS, based on Question 5 of the ZBPI by week
- Proportion of patients with $\geq 50\%$ reduction from Baseline in ADPS, based on Question 5 of the ZBPI by week
- Cumulative distribution function of percent change in ADPS based on Question 5 of the ZBPI from Baseline to Week 6 comparing each LX9211 treatment group to placebo
- Cumulative distribution function of percent change in ADPS based on Question 5 of the ZBPI from Week 6 to Week 11 comparing the LX9211 treatment group to placebo

3.4 Safety Variables

Safety endpoints are as follows:

CONFIDENTIAL

- Incidence of treatment-emergent AEs (TEAEs), suspected adverse reaction, AEs leading to discontinuation from the study, serious AEs (SAEs), and deaths
- Actual and change from Baseline in clinical laboratory results
- Actual and change from Baseline in vital signs results, including weight
- Clinically significant change from Baseline in physical examination (PE) findings
- Actual and change from Baseline in ECG findings

4. Pharmacokinetic (PK) /Pharmacodynamic (PD) Variables

The PK endpoints are the plasma C_{p2hr} and C_{trough} levels of LX9211 in patients with postherpetic neuralgia.

[REDACTED]

5. Analysis Populations

Analysis of the primary, secondary and other efficacy endpoints will be based on the modified Intent-to-Treat (mITT) population. Safety endpoints analyses will be based on the Safety Population.

5.1 Intent-to-Treat (ITT) Population

The ITT population will include all randomized patients.

5.2 Modified Intent-to-treat Population

The mITT population will include all randomized patients who take at least 1 dose of study drug during the double-blind Treatment Period. mITT patients will be analyzed according to their randomized treatment.

5.3 Per Protocol (PP) Population

The PP population will include patients in the mITT population who complete treatment through the primary assessment of the first 6 weeks, and did not have any important protocol deviations that would interfere with the collection or interpretation of the efficacy data.

Protocol deviations are defined as any change, divergence, or departure from the study design or procedures defined in the study protocol. Important protocol deviations are a subset of protocol deviations and may significantly impact the correctness, accuracy, and/or reliability of the study data or that may significantly

affect a patient's rights, safety, or well-being. [Section 5.3.1](#) details the types of deviations.

5.3.1 Important Protocol Deviations Leading to Exclusion from the PP Population Analysis

Only those important protocol deviations considered to have a major effect on efficacy will lead to complete exclusion of the patient from the PP population. For the purposes of this study, the following criteria have been identified as important protocol deviations leading to exclusion from the PP population as it is considered that the occurrences of any of these criteria might have an important influence on the primary efficacy endpoint.

Type	Important Protocol Deviation Leading to Exclusion from the PP population	Method of Identification
Prohibited Medication	Patients who take medications that are not permitted during the double-blind Treatment Period	Non-programmable review of blinded prior and concomitant medications listings [REDACTED] will provide the Medical Monitor with the lists of prior and concomitant medications taken by patients. The Medical Monitor will review this list and note any prohibited medications or therapies within 1 month prior to the Screening Visit. Patients will be excluded if they had prohibited medications or therapies within 1 month prior to the Screening Visit.
Entry Criteria Violations	Patients did not meet Inclusion Criterion 4 or Exclusion Criterion 4 or 7, which are thought to impact efficacy	Programmatic check based on eligibility data
Noncompliance During 6-week Double-blind Treatment Period	Patients who had low study drug compliance rate (<80%)	Programmatic check based on exposure and drug accountability data
Minimum Treatment Duration	Patients did not receive at least 5 weeks of double-blind treatment	Programmatic check based on the exposure data
Week 6 ADPS Missing	Patients did not have at least 4 ADPS scores within Week 6 in order to calculate weekly ADPS	Programmatic check of ADPS data
Errors in	Patients who received a wrong	Programmatic check based on

Statistical Analysis Plan Final v3.0

Lexicon Pharmaceuticals, Inc.
Protocol ID: LX9211.1.202-PHN

Labcorp Study ID: [REDACTED]

Treatment Allocation	treatment at 1 or more study visits due to packaging or dispensing errors during the double-blind Treatment Period	unblinded IRT database after the study is unblinded. The check will be done by comparing the kit number that IRT had assigned to the patient/visit against the kit number actually used.
Incorrect Stratum used in Randomization	Patients were randomized using an incorrect stratum	Programmatic check of IRT database compared to ADPS from Run-in
Clinical Trial Management System	[REDACTED] Clinical will provide the list of protocol deviations based on the clinical monitoring.	Non-programmable: The list will be reviewed prior to database lock and unblinding, and the important protocol deviations leading to exclusion from the PP population will be identified.

As defined in the table, a set of the important protocol deviations leading to exclusion from the PP population will be determined programmatically from the data. Those criteria which require clinical or medical monitoring interpretation will be reviewed prior to database lock.

All important protocol deviations occurring during the study will be reviewed and approved by Lexicon Pharmaceuticals, Inc. prior to database lock and unblinding. Should additional important protocol deviations leading to exclusion from the PP population, not anticipated at the time of preparing this SAP be identified during the study (and prior to unblinding), they will be provided in a separate document and included in all relevant protocol deviation reviews and approvals.

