7.3 Prohibited Medication

Use of any new medications prescribed or OTC for treatment of PHN pain is not permitted during the course of the study. Only the acetaminophen provided by the Sponsor as a rescue medicine may be used during the course of the study. The use of personally acquired acetaminophen is prohibited. Use of any opioid medication for the management of PHN within the 2 months prior to Screening is not permitted. **Note:** Brief use (<1 week) of opioid medication for management of non-PHN acute pain (eg, tooth extraction/acute injury) ≥ 2 months prior to Screening Visit is permitted.

All medications, including the study drug, taken by patients during the study will be captured in the source documents and recorded on the eCRF.

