7.4.2 Prior and Concomitant Medications

Medications received prior to or concomitantly with study drug will be coded using the World Health Organization (WHO) Drug Dictionary (Version B3 Sep2020 or a later version if updated during the study]), Anatomical Therapeutic Chemical (ATC) Classification codes.

Prior medications and concomitant medications are defined as follows:

- Prior medications are those taken prior to the first dose date of double-blind treatment, and with a stop date before first dose date of double-blind treatment.
- Concomitant medications are those with a start date on or after the first dose date of double-blind treatment, or those with a start date before the first dose date of double-blind treatment and a stop date on or after the first dose date of double-blind treatment.

If a medication cannot be classified as “prior” or “concomitant” after applying imputation rules for missing/incomplete dates, it will be classified as concomitant.

Prior medications, concomitant medications taken during double-blind Treatment Period (excluding prohibited and rescue concomitant medications), prohibited concomitant medications taken during double-blind Treatment Period, and concomitant medications started during Safety Follow-up Period (those medications starting after the last dose of double-blind study drug and through the end of the patient's Safety Follow-up Period) will be summarized separately by treatment group and overall for the mITT population.

The number and percentage of patients using each medication will be displayed together with the number and percentage of patients using at least 1 medication within each therapeutic class (ATC-Level 2), chemical subgroup (ATC-Level 4), and generic term.

The percentage of patients who need rescue medication during the double-blind Treatment Period will be summarized descriptively by treatment group and overall for the mITT population.

Prior medications, concomitant medications and rescue concomitant medications will be listed separately.

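### SAP 5.3.1: the per-protocol row for prohibited medication during double-blind treatment gives an identification method that looks only at the month before Screening

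*SAP*

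**What the plan says.** SAP 5.3 takes the PP set from mITT patients who complete the six weeks without an important deviation. The table in 5.3.1 lists those deviations, with one column for the deviation and one for how it is identified.

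In the Prohibited Medication row, the deviation column reads "Patients who take medications that are not permitted during the double-blind Treatment Period". The method column describes a "Non-programmable review of blinded prior and concomitant medications listings". It then instructs: "The Medical Monitor will review this list and note any prohibited medications or therapies within 1 month prior to the Screening Visit". It closes with the exclusion rule: "Patients will be excluded if they had prohibited medications or therapies within 1 month prior to the Screening Visit".

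Two other rows bear on the point. The entry-criteria row covers "Patients did not meet Inclusion Criterion 4 or Exclusion Criterion 4 or 7, which are thought to impact efficacy"; Exclusion Criterion 8, the protocol's criterion on prohibited medications and therapies, is not among them. The Clinical Trial Management System row says that "Clinical will provide the list of protocol deviations based on the clinical monitoring", and PP exclusions are to be picked from that list before lock and unblinding.

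The prohibition itself covers the whole trial. Protocol 7.3 states: "Use of any new medications prescribed or OTC for treatment of PHN pain is not permitted during the course of the study". SAP 7.4.2 gives "prohibited concomitant medications taken during double-blind Treatment Period" a summary of its own.

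**The concern.** The two cells of one row name different periods, and the cell that tells the Medical Monitor what to do names the wrong one for this deviation. The pre-Screening window appears at both steps, flagging and exclusion. No step in the row tells anyone to flag use during Weeks 1 to 6, although the concomitant-medication listing is supplied.

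A new analgesic taken on treatment can move a pain score directly. The planned efficacy analyses offer little else on this. The primary analysis in SAP 7.6.1 keeps all observed data, including data after rescue. The supplementary model in SAP 7.6.3 drops data after rescue medication, which under the protocol is sponsor-supplied acetaminophen. No analysis in 7.6.3 addresses prohibited medication. The PP repeat of the primary model is where its influence would be expected to show, so the set should be built by a method that finds it.

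**Working it through.** The plan gives no figure to reproduce. The check compares date windows and then sets the two cells side by side.

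**Inputs**
- Screening target Day -28 and Run-in target Day -14 (SAP Table 1.2).
- Baseline diary window Day -7 to Day -1; Week 6 diary window Days 36 to 42 (SAP Table 1.1).
- No Day 0 (SAP 6.1).
- Assumption: one month is 30 days, with 28 to 31 as the range.

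**Window that the method checks**
- Last day: -28 - 1 = Day -29.
- First day: -28 - 30 = Day -58 (range: -28 - 28 = Day -56 to -28 - 31 = Day -59).

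**Window that the deviation names**
- Day 1 to Day 42.

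**Overlap**
- Zero days. Day -28 to Day -1, which is 28 days, lies between the two windows.
- A shorter Screening Period does not change this. If Screening took no time at all, the Screening Visit would fall at about Day -14, where Run-in starts. The checked window would then end on Day -15, still 14 days before treatment.
- At target days, the span in which newly started prohibited use goes unflagged by this row is Day -28 to Day 42: 28 + 42 = 70 days.

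**The two cells applied to four patterns of prohibited use**

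| Pattern | Deviation cell | Method cell |
|---|---|---|
| Started in Week 3 of treatment | Excluded | Not flagged |
| Used in the month before Screening and continued on treatment | Excluded | Excluded |
| Last used three weeks before Screening, none later | Not covered | Excluded |
| Used only in Run-in Week 2 | Not covered | Not flagged |

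The cells agree that a patient is excluded only where use before Screening carried on into treatment. The fourth pattern is reached by neither cell, although Run-in Week 2 supplies the baseline score.

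**The third pattern against the protocol**
- Exclusion Criterion 8 (synopsis and Section 6.2) requires prohibited interventions used for neuropathic pain to be stopped at least 1 month before Screening. Under that text, this patient breached an entry criterion.
- The Screening Period paragraph of the synopsis asks for a washout of at least 2 weeks before Screening for prohibited non-opioid medications. Under that text, three weeks complies.
- Whether the exclusion is proper therefore depends on which protocol passage applies, and the two disagree.

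**Weight of one patient**
- With 37 planned per arm, one misplaced patient is 1/37 = 2.7% of an arm.

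**The case against.** The strongest reply is that on-treatment use is still a named PP exclusion. The column heading says that the listed deviations lead to exclusion, and nothing says that the method cell overrides the deviation cell. The Medical Monitor receives the concomitant listing, so the information is in view. Deviations recorded in monitoring can also lead to exclusion, the sponsor reviews all important deviations before lock, and further PP-excluding deviations can be added before unblinding.

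Much of this stands. A reader might infer that patients who take prohibited drugs on treatment will stay in the PP set. The documents do not support that certainty: they may stay, depending on how the conflict is read and what the other reviews find. The safeguards are weaker than a stated rule, however. The monitoring row gives no medication criterion and no window. The clause on added deviations is for those not foreseen when the SAP was written, and this one was foreseen, since it has its own row.

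A reader might also infer that pre-Screening users are wrongly discarded. That is not shown. The one-month window matches Exclusion Criterion 8, and removing patients who breached an entry criterion is an ordinary function of a PP set. The check sits under the wrong deviation, but it has a source.

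Finally, PP analyses are supportive and exploratory under SAP 7.6, and SAP 7.4.2 already reports prohibited on-treatment use by arm. Both points are right and limit the importance of the matter.

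**Conclusion.** The row is internally inconsistent and should be corrected. As written, its method cannot identify prohibited use that begins after Screening, because the checked and intended windows share no day under any reading of one month between 28 and 31 days or any permitted length of Screening. Whether such patients actually remain in the PP set depends on the monitoring and pre-lock reviews, so the defect is a stated rule that does not do its job, not a demonstrated error in the set.

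The number of patients concerned depends on how often prohibited medication is used, which the documents do not give; the effect on the PP estimate cannot be quantified. It would be too strong to say that the trial's main conclusion is at risk: the primary mITT estimate and test do not use the PP set.

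**What to change.** Reword the method cell so that the Medical Monitor flags, from the blinded prior and concomitant listings already supplied, any prohibited medication or therapy used from the first double-blind dose to the end of the Week 6 diary window (Day 42). Consider extending the check to Run-in Week 2 (Day -7 to Day -1), since use there would alter the baseline; if that is adopted, the deviation cell should say so too.

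If pre-Screening use is also meant to exclude, list it as a separate entry-criterion row tied to Exclusion Criterion 8. Before doing so, reconcile the synopsis washout of at least 2 weeks with the at least 1 month in Exclusion Criterion 8, so that a patient who followed one passage is not counted as a deviator under the other. Which period should apply is for the sponsor to settle.

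The cost is one SAP table cell, with one further row if wanted, plus the washout reconciliation in the protocol. The listings and the reviewer stay the same, and no new data are needed. The change should be made before unblinding.
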